14 COMPLIANCE, AUDIT AND PROTOCOL DEVIATIONS

14.1 Good Clinical Practice

This study will be conducted in accordance with the protocol, the Sponsor's standard operating procedures, national regulatory requirements, provisions of the relevant ethics committees and Good Clinical Practice (GCP) principles.

14.2 Audits

The study may be subject to audit by NHS Greater Glasgow and Clyde under their remit as Sponsor.

14.3 Protocol Deviation Reporting

A protocol deviation is any departure from the approved protocol. All deviations will be recorded and reported to the sponsor. The sponsor will not authorize prospective protocol deviations/waivers, unless the deviation is necessary to eliminate an immediate hazard.

15 PATIENT AND PUBLIC INVOLVEMENT

A group of patients with mesothelioma and relatives of patients who have previously been diagnosed with mesothelioma were consulted for their views on the overall study premise and study design. Patient facing documentation was also reviewed by these two groups.

16 DATA HANDLING

Data generated by the study will be stored in a linked anonymised fashion in a password-protected computer. Subject paper notes will be stored in a locked filing cabinet in a locked office of a secure building.

16.1 Case Report Forms

Entries to the CRFs will be made in black ballpoint pen and must be legible. Any errors must be crossed out with a single stroke, the correction inserted and the change initialled and dated by the Investigator. Correction fluid must not be used. All data submitted on CRFs are verifiable in the source documentation or that any discrepancies are recorded and explained.

Trial sites should keep a copy of all completed CRFs. The original CRFs should be returned to the Pleural Disease Unit, Queen Elizabeth University Hospital for data entry and computation of relevant end-points and ultimately, statistical analysis. CRFs from the trial will be stored in line with current regulatory requirements. Other essential documents, including source data, consent forms, and regulatory documentation, will be archived by the Investigator, in an appropriate archive facility in line with current regulatory requirements and made available for monitoring, audit and regulatory inspection as required.

The end of the trial should be outlined clearly, below is sample text.

The study will end when the steering committee agrees that one or more of the following situations applies:

- Last patient last study visit;

OR

- i. The planned sample size has been achieved;
- ii. The Independent Data Monitoring Committee has advised discontinuation, e.g. because of safety concerns about the trial, or a statistically significant difference in clinical outcomes is evident between the two treatment arms;
- iii. There is insufficient funding to support further recruitment, and no reasonable prospect of additional support being obtained;

- iv. New information makes it inappropriate to continue to randomise patients to one or other arm of the trial;

Recruitment is so poor that completion of the trial cannot reasonably be anticipated

17. Protocol Amendments

Any change in the study protocol will require an amendment. Any proposed protocol amendments will be initiated by the CI following discussion with the Sponsor and any required amendment forms will be submitted to the, ethics committee and sponsor. The CI will liaise with study sponsor to determine whether an amendment is non-substantial or substantial. All amended versions of the protocol will be signed by the CI and Sponsor representative. Before the amended protocol can be implemented favourable opinion/approval must be sought from the original reviewing REC and Research and Development (R&D) office(s).

17. Ethical Consideration

The study will be carried out in accordance with the World Medical Association Declaration of Helsinki (1964) and its revisions.

Favourable ethical opinion will be sought from an appropriate REC before patients are entered into this clinical trial. **Patients will only be allowed to enter the study once either they have provided written informed consent.** The CI will be responsible for updating the Ethics committee of any new information related to the study.

17. Finance and Indemnity

Brief details on how the study is funded should be included here.

NHS employed researchers will be covered for negligent harm through the NHS CNORIS indemnity scheme. If you are a University employee you may need extra cover for non-negligent harm through your University. Please check this with your Research and Enterprise department.

Example text: The XXX study is sponsored by NHS Greater Glasgow & Clyde. The sponsor will be liable for negligent harm caused by the design of the trial. NHS indemnity is provided under the Clinical Negligence and Other Risks Indemnity Scheme (CNORIS).

17. Publications

Study results whether, negative or positive, should be disseminated. Details of your plan for dissemination should be included here.

18 . REFERENCES

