1 STUDY SYNOPSIS

Study Title	EXercise TheRApy in Mesothelioma – A feasibility study (EXTRA-Meso feasibility study)
Study Sponsor	NHS Greater Glasgow and Clyde
Study Design	Randomised feasibility trial
Number of Patients	40
Patient Population	Patients with a diagnosis of mesothelioma
Primary Objective	To determine the feasibility of recruiting patients with mesothelioma to a randomised trial of exercise therapy, in order to inform design of a future phase 3 trial
Secondary Objectives	
 1. To determine barriers to study recruitment 2. To determine barriers to study retention 3. To determine safety and tolerability of the exercise programme intervention and study assessments
Primary Outcome Measure	Number of patients recruited
Secondary Outcome Measures	
 1. Proportion of screened patients who are ineligible 2. Reasons for study ineligibility 3. Study drop-out rate 4. Reasons for study drop-out 5. Intervention adherence rate 6. Adverse events 7. Health-related Quality of Life (HRQoL) questionnaire completion rate 8. Framework analysis from qualitative interviews
Eligibility Criteria	
Inclusion Criteria:
 
 1. Diagnosis of mesothelioma, ratified by a mesothelioma MDT 2. Performance status 0 -2 3. Clinical frailty score ≤ 5 4. Informed written consent 
Exclusion Criteria:
 
 1. Performance status ≥ 3 2. Clinical frailty score ≥ 6

	3. Unlikely to be able to participate in an exercise programme (clinician/physiotherapist judgement)
Screening and Consent	Patients with mesothelioma will be identified at mesothelioma MDTs, routine respiratory/oncology outpatient appointments, and during inpatient reviews. Those meeting all eligibility criteria will be provided with a Patient Information Sheet (PIS) and given sufficient time to consider participation.
Randomisation and Allocation	Following consent and baseline assessments, patients will be randomised using an online system (sealedenvelope.com) and allocated 1:1 using random permuted blocks to one of two groups: 
 A. Exercise Therapy B. Standard Care
End of Study	Trial participation will end when the last patient has completed their 26 week visit
Study duration	18 months

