10 STATISTICAL ANALYSIS PLAN

We will use descriptive statistics to describe the demographics and clinical characteristics of the study population. Means (with standard deviations) or medians (with inter-quartile ranges) will be used to summarise continuous variables, depending on their distribution and proportions to summarise categorical variables.

Total recruitment, recruitment rate, study drop-out rate and intervention adherence rate will be reported by simple descriptive statistics, or proportions where appropriate.

Semi-structured interviews will be analysed using Framework Analysis¹⁹, which will involve a five-step process:

1. Familiarisation with the data
2. Identifying a thematic framework
3. Indexing
4. Charting
5. Mapping and interpretation

The analysis will be predominantly deductive, as it will specifically focus on facilitators and barriers to study retention, and to the uptake and experience of the exercise intervention.

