11 END OF TRIAL

Trial recruitment will terminate either 12 months after opening or after 40 patients have been recruited, whichever is soonest. Trial participation will cease once the final patient has completed their 26-week follow-up.

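### Does the sample text left in section 16.1 create a second end-of-study rule that could cut the feasibility data short?

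*Combined protocol and SAP*

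**What the plan says.** Section 11 closes recruitment at 12 months or at 40 patients, whichever comes first, and then states: "Trial participation will cease once the final patient has completed their 26-week follow-up". The synopsis agrees: "Trial participation will end when the last patient has completed their 26 week visit". It gives the study duration as 18 months.

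Section 16.1 turns from handling case report forms to a drafting note: "The end of the trial should be outlined clearly, below is sample text". The text under that note begins "The study will end when the steering committee agrees that one or more of the following situations applies". Its first option is the last patient's last study visit. After an OR come the alternatives:

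- item (i): "The planned sample size has been achieved";
- item (ii): advice from an Independent Data Monitoring Committee to discontinue, with safety concerns or "a statistically significant difference in clinical outcomes is evident between the two treatment arms" given as examples of the reason;
- items (iii) and (iv): lack of funding for further recruitment, and new information that makes further randomisation inappropriate;
- an unnumbered last line: "Recruitment is so poor that completion of the trial cannot reasonably be anticipated".

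Section 10 plans description only: "Total recruitment, recruitment rate, study drop-out rate and intervention adherence rate will be reported by simple descriptive statistics, or proportions where appropriate". Section 13 bases the decision on a phase 3 trial on two metrics, total recruitment and adherence. Adherence means at least 18 exercise sessions in the 12-week programme.

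**The concern.** On a first reading the protocol has two end-of-study rules, and no sentence says which prevails. Three of the extra triggers fit this study badly.

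- **Item (i)** appears to end the study at the point where section 11 ends only recruitment. Applied that way, it would leave follow-up, questionnaire completion and adherence incomplete for late recruits.
- **Item (ii)** mentions statistical significance, although section 10 plans no between-arm test and no interim look.
- **The poor-recruitment line** has no threshold, although the number recruited is the primary outcome and section 13 already grades it.

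Adherence and recruitment are the two section 13 criteria, so a shortened study could change the grading. Drop-out would suffer too. It is not a section 13 criterion, but a secondary outcome that section 6.3 uses to plan the phase 3 trial.

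**Working it through.** **1. Which rule gives the plan's own duration?** Inputs: 12 months of recruitment at most (section 11), 26 weeks of follow-up (section 11 and synopsis), and 365.25/12/7 = 4.348 weeks per month. Duration = 12 + 26/4.348 = 12 + 5.98 = 17.98 months. This reproduces the synopsis figure of 18 months. Ending the study at the 40th recruit would give 12 months at most.

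**2. What would item (i) do if applied literally?** Assumptions, not in the documents: 40 patients enter evenly over T weeks, patient k at week kT/40, and the study stops at the 40th entry. Patient k then has T(40 − k)/40 weeks of follow-up. The exercise programme starts at week 1 and lasts 12 weeks (sections 9.2 and 9.4), so it ends at about week 13. At 3 sessions a week, 18 sessions take 18/3 = 6 weeks, so adherence can be reached by about week 7.

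Patients out of 40 with less follow-up than needed:

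| T (weeks) | under 26 weeks | under 16 weeks | under 13 weeks | under 7 weeks |
|---|---|---|---|---|
| 52 | 20 | 13 | 10 | 6 |
| 39 | 27 | 17 | 14 | 8 |
| 26 | 40 | 25 | 20 | 11 |

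Spacing the entries from week 0 instead, at (k − 1)T/39, changes a count by at most one. About half of each count is in the exercise arm: at T = 52, about 5 of 20 would not have finished the programme and about 3 of 20 could not yet have reached 18 sessions.

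Suppose true adherence is 60% (an assumption) and unfinished patients count as non-adherent. At T = 52 the observed figure would lie between 0.60 × (1 − 10/40) = 45% and 0.60 × (1 − 6/40) = 51%, on either side of the 50% Green limit. Item (i) costs no recruitment, because section 11 also stops at 40.

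**3. What would the poor-recruitment line do?** A steady pace that reaches 20 to 39 patients at month 12 (Green) gives 20/2 = 10 to 39/2 = 19.5 at month 6, so 10 to 19 patients (Amber). But section 11 lets the trial complete at 12 months with fewer than 40 patients. A trial on course for 20 to 39 is therefore heading for completion, and the line would reach it only if completion were taken to mean 40.

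**4. Can the block be applied at all?** Every trigger needs a steering committee to agree, and item (ii) also needs advice from a data monitoring committee. Neither body appears anywhere else in the available text. Items (iii), (iv) and the last line all speak of recruiting or randomising further patients. In that company item (i) reads naturally as closing recruitment at 40, which is the section 11 rule. Finally, the options are alternatives and the first is last patient last visit, so a study run to section 11 also meets the block.

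**The case for a change.** The best case for acting is that this text stands in the approved protocol. Section 14.3 treats any departure from the protocol as a deviation, and the section on amendments requires an amendment for any change, so a conflict should not be settled by tacit agreement. Nothing marks where the sample text stops, and it sits between operative rules on record keeping and on amendments. The lead-in speaks of the study ending, not of recruitment closing. Removal would be cheap. The block also holds the only mention in the available text of stopping the study for safety, funding or new information, and of any oversight committee.

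What stands is that the inconsistency is real, the accrual arithmetic is right on its assumptions, and the block is worth tidying when the document is next revised. What does not stand is the step to harm. The opening note identifies the list as sample wording, and section 11 already supplies the definition that the note asks for. Similar template remnants under Finance and Indemnity and under Publications support reading the block as an editing leftover. Following section 11 is not a departure from the protocol. Whether to say more about study-level discontinuation or committees is a matter of writing down missing detail. It does not alter the design, the sample size or any analysis in section 10.

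**Conclusion.** No change to the plan is needed. Section 11, the synopsis and the 18-month duration agree on one operative rule, and the conflicting list is leftover template wording under an unrelated heading. With that rule followed, the end-of-study rule cuts no patient's follow-up short, and the effect on recruitment, adherence, drop-out and the section 13 grading is zero.

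The losses calculated for item (i) arise only if several things happen together: labelled sample text is treated as binding, a steering committee is formed and agrees, 40 patients are reached, and the item is read as ending the study and not just recruitment. Their size then depends on the assumed even accrual. The poor-recruitment line needs a strained reading of completion before it touches a study that section 13 would grade Green. Item (ii) turns on committee advice, with significance only as an example, so it does not bring a between-arm test into the analysis. The conclusion rests on the sponsor running the trial to its own End of Trial section, which is the ordinary reading of the document.
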